7.1 Definition of AE

AE Definition

• An AE is any untoward medical occurrence in a patient or clinical study patient, temporally associated with the use of study intervention, whether or not considered related to the study intervention.• NOTE: An AE can therefore be any unfavorable and unintended sign (including an abnormal laboratory finding), symptom, or disease (new or exacerbated) temporally associated with the use of study intervention.

Events Meeting the AE Definition

• Any abnormal laboratory test results (hematology, clinical chemistry, or urinalysis) or other safety assessments (e.g., ECG, radiological scans, vital sign measurements), including those that worsen from baseline, considered clinically significant in the medical and scientific judgment of the investigator. Any abnormal laboratory test results that meet any of the conditions below must be recorded as an AE:
• Is associated with accompanying symptoms;• Requires additional diagnostic testing or medical/surgical intervention;• Leads to a change in study dosing (outside of any protocol-specified dose adjustments) or discontinuation from the study, significant additional concomitant drug treatment, or other therapy.• Exacerbation of a chronic or intermittent preexisting condition including either an increase in frequency and/or intensity of the condition.• New conditions detected or diagnosed after study treatment administration even though it may have been present before the start of the study.• Signs, symptoms, or the clinical sequelae of a suspected drug-drug interaction.• Signs, symptoms, or the clinical sequelae of a suspected overdose of either study intervention or a concomitant medication. Overdose per se will not be reported as an AE/SAE unless it is an intentional overdose taken with possible suicidal/self-harming intent. Such overdoses should be reported regardless of sequelae.

- The signs, symptoms, and/or clinical sequelae resulting from lack of efficacy will be reported as an AE or SAE if they fulfill the definition of an AE or SAE and meet the requirements as per [Section 7.4.8.1](#). Also, “lack of efficacy” or “failure of expected pharmacological action” does not constitute an AE or SAE.

Events **NOT** Meeting the AE Definition

- Any clinically significant abnormal laboratory findings or other abnormal safety assessments which are associated with the underlying disease, unless judged by the investigator to be more severe than expected for the patient’s condition.
- The disease/disorder being studied or expected progression, signs, or symptoms of the disease/disorder being studied, unless more severe than expected for the patient’s condition.
- Medical or surgical procedure (e.g., endoscopy, appendectomy): the condition that leads to the procedure is the AE.
- Situations in which an untoward medical occurrence did not occur (social and/or convenience admission to a hospital).
- Anticipated day-to-day fluctuations of preexisting disease(s) or condition(s) present or detected at the start of the study that do not worsen.
- Worsening of signs and symptoms of the malignancy under study should be recorded as AEs in the appropriate section of the CRF. Disease progression assessed by measurement of malignant lesions on radiographs or other methods should not be reported as AEs.

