5.2. Exclusion Criteria

Patients meeting any of the following criteria are not eligible for enrollment in the study.

1. Patients with symptomatic brain metastasis (e.g., have neurologic symptoms related to brain metastases).
2. Prophylactic or preventive anti-epileptic therapy.
Note: Anti-epileptic therapy indicated in order to prevent neurologic symptoms caused by a preexisting condition and not related to brain metastasis is allowed.
3. Known hypersensitivity or contraindication to any component of study treatment or their excipients.
4. Inability to swallow and retain study treatment.
5. Uveal or mucosal melanoma.
6. History of or current leptomeningeal metastases.
7. Treatment with SRS or craniotomy within 14 days prior to start of study treatment, or treatment with whole-brain radiation within 28 days prior to study treatment. Patients who received local therapy should have complete recovery with no neurological sequelae.

8. Either of the following:
 - a. Radiation therapy to non-brain visceral metastasis within 2 weeks prior to start of study treatment;
 - b. Continuous or intermittent small-molecule therapeutics or investigational agents within 5 half-lives of the agent (or within 4 weeks prior to start of study treatment, when half-life is unknown).
9. Patients treated in the adjuvant setting with BRAF or MEK inhibitor(s) < 6 months prior to enrollment. Patients who received BRAF or MEK inhibitors in the metastatic setting are excluded.
10. Is currently participating in a study and receiving an investigational agent; has received an investigational agent or used an investigational device within 14 days prior to start of study treatment.
11. Patients who have undergone major surgery (e.g., inpatient procedure with regional or general anesthesia) \leq 6 weeks prior to start of study treatment. For minor surgical procedures \leq 6 weeks prior to start of study treatment, consult the Sponsor Medical Monitor.
12. Patient has not recovered to \leq Grade 1 from toxic effects of prior therapy before starting study treatment.
Note: Stable chronic conditions (\leq Grade 2) that are not expected to resolve (such as neuropathy, myalgia, alopecia, prior therapy-related endocrinopathies) are exceptions and patients with these may enroll.
13. Impaired cardiovascular function or clinically significant cardiovascular disease including, but not limited to, the following:

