7.4.7. Disease-Related event and/or Disease-Related Outcomes Not Qualifying as AEs or SAEs

Not applicable

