7.2 Definition of SAE

If an event is not an AE per definition above, then it cannot be an SAE even if serious conditions are met (e.g., hospitalization for signs/symptoms of the disease under study, death due to progression of disease).

An SAE is defined as any untoward medical occurrence that, at any dose:
a. Results in death
b. Is life-threatening The term “life-threatening” in the definition of “serious” refers to an event in which the patient was at risk of death at the time of the event. It does not refer to an event that hypothetically might have caused death if it were more severe.
c. Requires inpatient hospitalization or prolongation of existing hospitalization In general, hospitalization signifies that the patient has been detained (usually involving at least an overnight stay) at the hospital or emergency ward for observation and/or treatment that would not have been appropriate in the physician’s office or outpatient setting. Complications that occur during hospitalization are AEs. If a complication prolongs hospitalization or fulfills any other serious criteria, the event is serious. When in doubt as to whether “hospitalization” occurred or was necessary, the AE should be considered serious. Hospitalization for elective treatment of a preexisting condition that did not worsen from baseline is not considered an AE.
d. Results in persistent disability/incapacity 
• The term disability means a substantial disruption of a person’s ability to conduct normal life functions.• This definition is not intended to include experiences of relatively minor medical significance such as uncomplicated headache, nausea, vomiting, diarrhea, influenza, and accidental trauma (e.g., sprained ankle) which may interfere with or prevent everyday life functions but do not constitute a substantial disruption.
e. Is a congenital anomaly/birth defect

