f. Other situations: 
• Medical or scientific judgment should be exercised in deciding whether SAE reporting is appropriate in other situations such as important medical events that may not be immediately life-threatening or result in death or hospitalization but may jeopardize the patient or may require medical or surgical intervention to prevent one of the other outcomes listed in the above definition. These events should usually be considered serious.• Examples of such events include invasive or malignant cancers, intensive treatment in an emergency room or at home for allergic bronchospasm, blood dyscrasias or

convulsions that do not result in hospitalization, or development of drug dependency or drug abuse.

- Progression of the malignancy under study (including signs and symptoms of progression) should not be reported as an SAE unless the outcome is fatal within the active collection period. Hospitalization due to signs and symptoms of disease progression should not be reported as an SAE. If the malignancy has a fatal outcome during the study or within the active collection period, then the event leading to death must be recorded as an AE on the CRF, and as an SAE with CTCAE Grade 5 (see the Assessment of Intensity section).

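### Appendix 7.1 both excludes and calls for recording as an AE a worsening of disease symptoms that is judged expected, so Phase 2 all-causality TEAE counts can depend on which line a site follows

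*Protocol*

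**What the plan says.** Two bullets in Protocol Appendix 7.1 stand in one list, under the heading "Events NOT Meeting the AE Definition".

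- The second bullet takes out "expected progression, signs, or symptoms of the disease/disorder being studied, unless more severe than expected" for the patient's condition.
- The last bullet says "Worsening of signs and symptoms of the malignancy under study should be recorded as AEs in the appropriate section of the CRF". It sets no severity condition. It then adds that "Disease progression assessed by measurement of malignant lesions on radiographs or other methods should not be reported as AEs".

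The first bullet of the list has the same form as the second. It takes out clinically significant abnormal laboratory or other safety findings that go with the underlying disease, unless the investigator judges them worse than expected.

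Three other places bear on the question:

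- Protocol Section 7.4.7 is titled "Disease-Related event and/or Disease-Related Outcomes Not Qualifying as AEs or SAEs", and its whole content is that it does not apply.
- Protocol Section 7.3.3 has treatment-emergent abnormal findings on physical examination recorded as AEs, with no exception for disease.
- SAP Section 6.6.1 bases the AE tables on TEAEs. It takes seriousness, grade and action taken from the AE page of the CRF. SAP Section 3.4.1 defines a TEAE by timing alone.

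**The concern.** AE incidence and severity is a secondary endpoint of the study and part of the primary endpoint of the Safety Lead-in (Protocol Section 3). If the recording rule gives two answers for the same event, the reported rate depends partly on which line each site applied, and up to 75 centers may apply it.

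The gap matters more here than in most oncology trials because of the population. Exclusion criterion 1 removes "Patients with symptomatic brain metastasis (e.g., have neurologic symptoms related to brain metastases"). Any later neurological symptom caused by the brain disease is therefore new or worse. If the investigator judges it expected for a patient whose brain disease is advancing, it falls exactly where the two bullets disagree.

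Such events can occur while AEs are being collected. Section 6.8 lets treatment continue after progression in one compartment, and Section 7.4.1 runs active collection to at least 30 days after the last dose. An event that is never entered on the AE page cannot be recovered at analysis.

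**Working it through.** No stated figure needs to be reproduced. The check is a comparison of texts, followed by arithmetic on the planned cohort size.

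**Step 1. Apply each bullet to each kind of event.**

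| Event | Exclusion bullet | Last bullet | Agree? |
|---|---|---|---|
| Disease symptom, unchanged | Not an AE | No worsening, so nothing to record | Yes |
| Worsening beyond what is expected | AE | AE | Yes |
| Worsening judged expected | Not an AE | AE | **No** |
| Expected progression seen only by lesion measurement | Not an AE | Not an AE | Yes |

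The conflict is confined to the third row.

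**Step 2. Look for a rule that ranks the bullets.** There is none. The recording instruction itself stands under the heading for events that are not AEs, so its position gives it no priority. Sections 7.4.7 and 7.3.3 both fit poorly with the exclusion, but neither says that it yields.

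**Step 3. Look for a remedy in the SAP.** TEAEs are counted as recorded. Neurological symptom data appear only as a listing (SAP Section 6.6.6), so no summary rate exists against which to check the AE tables.

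**Step 4. Trace what is and is not affected.**

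- BMRR does not use AE data.
- DLTs exclude events explained by the disease or its progression (Protocol Section 6.6, Table 7), whichever bullet is followed. The Lead-in decision had already been made on 3 DLTs in 9 evaluable patients when SAP version 2.0 was written (SAP Section 2).
- SAE status depends on AE status: "If an event is not an AE per definition above, then it cannot be an SAE even if serious conditions are met". Appendix 7.2 separately says "Hospitalization due to signs and symptoms of disease progression should not be reported as an SAE", so non-fatal symptoms of progression stay out of SAEs under either bullet.
- TEAEs judged treatment-related are tabulated separately in SAP Section 6.6.1, so symptoms attributed to disease drop out of those tables either way.

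What remains is all-causality TEAE incidence and grade in Phase 2, largely for non-serious events. This includes the all-causality tables of Grade 3 or higher events and of events leading to dose changes or discontinuation.

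**Step 5. Scale per patient.**

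- One patient in a cohort of 50: 1/50 = 2 percentage points.
- SAP Section 6.6.1 uses a 10% threshold for the common-TEAE table: 0.10 × 50 = 5 patients.
- At that boundary, 4/50 = 8% and 5/50 = 10%, so one reclassified patient can add or drop a preferred term.

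**The case against.** The strongest reply is that the surrounding text favors recording. The last bullet is specific to the malignancy under study and says both what to record and what not to. The AE definition covers a symptom that is new or exacerbated, and the list excludes fluctuations of preexisting conditions only where they do not worsen. A careful site could conclude that the last bullet governs. That is a reasonable reading, but the text does not state it, and the exclusion bullet stands beside it with equal force. The wording is also that worsening *should* be recorded, which is weaker than *must*.

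It can also be said that safety is summarized descriptively, with no AE hypothesis and no formal comparison between cohorts. This stands. No test or decision rule is compromised; only the meaning of the reported rates is.

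A reader might infer that Section 7.4.7 adds a third, competing rule. It does not. If its entry means that no disease-related events are exempt, it supports the recording bullet and conflicts only with the exclusion.

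A reader might also try to size the problem. If 50% to 75% of patients had brain progression during AE collection and 20% to 40% of those had symptoms, 0.50 × 0.20 = 10% to 0.75 × 0.40 = 30% of patients would be affected. The documents support neither input. The brain PFS of 3.7 to 4.0 months in Section 2.1.3 is for BRAF-inhibitor monotherapy, and the 6.5 months is response duration among responders to a different combination. Recording of non-serious AEs also stops at new anticancer therapy (Section 7.4.1.2). The range further assumes that every such event is judged expected and that all sites follow the same bullet.

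**Conclusion.** The contradiction is real and stands in the current text. A worsening of disease symptoms that is judged expected is both not an AE and an AE, and neither the Protocol nor the SAP settles which. The reach is narrow: mainly Phase 2 all-causality TEAE incidence and grade, largely non-serious.

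The number of patients involved cannot be estimated from the documents. Only the effect per patient can be given: 2 points in a cohort of 50, with 5 patients marking the 10% table threshold.

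The link to neurological events is an inference, since Appendix 7.1 names none. It rests on the entry criterion and on investigators judging some of these symptoms expected. A reader might infer that the Lead-in safety decision or SAE reporting of non-fatal progression is in doubt. The documents do not support that, because separate rules govern both whichever bullet is followed.

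**What to change.** Reconcile the passages into one recording rule. One way to do it:

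- Limit the exclusion to progression assessed by lesion measurement.
- Move the sentence on recording worsened signs and symptoms to the list of events that meet the AE definition.
- Bring the parallel first bullet, on abnormal safety findings, and Section 7.4.7 into line with that rule.
- Send sites a memo stating the rule.

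Showing TEAEs with and without disease-attributed events is optional. It would need attribution to disease to be captured consistently, as well as an extra table.

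The cost is Protocol wording and the memo. Under this version of the rule, all-causality AE counts may rise, and events recorded before the change may not be comparable with those recorded after it.

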7.2 Definition of SAE

If an event is not an AE per definition above, then it cannot be an SAE even if serious conditions are met (e.g., hospitalization for signs/symptoms of the disease under study, death due to progression of disease).

An SAE is defined as any untoward medical occurrence that, at any dose:
a. Results in death
b. Is life-threatening The term “life-threatening” in the definition of “serious” refers to an event in which the patient was at risk of death at the time of the event. It does not refer to an event that hypothetically might have caused death if it were more severe.
c. Requires inpatient hospitalization or prolongation of existing hospitalization In general, hospitalization signifies that the patient has been detained (usually involving at least an overnight stay) at the hospital or emergency ward for observation and/or treatment that would not have been appropriate in the physician’s office or outpatient setting. Complications that occur during hospitalization are AEs. If a complication prolongs hospitalization or fulfills any other serious criteria, the event is serious. When in doubt as to whether “hospitalization” occurred or was necessary, the AE should be considered serious. Hospitalization for elective treatment of a preexisting condition that did not worsen from baseline is not considered an AE.
d. Results in persistent disability/incapacity 
• The term disability means a substantial disruption of a person’s ability to conduct normal life functions.• This definition is not intended to include experiences of relatively minor medical significance such as uncomplicated headache, nausea, vomiting, diarrhea, influenza, and accidental trauma (e.g., sprained ankle) which may interfere with or prevent everyday life functions but do not constitute a substantial disruption.
e. Is a congenital anomaly/birth defect
f. Other situations: 
• Medical or scientific judgment should be exercised in deciding whether SAE reporting is appropriate in other situations such as important medical events that may not be immediately life-threatening or result in death or hospitalization but may jeopardize the patient or may require medical or surgical intervention to prevent one of the other outcomes listed in the above definition. These events should usually be considered serious.• Examples of such events include invasive or malignant cancers, intensive treatment in an emergency room or at home for allergic bronchospasm, blood dyscrasias or

convulsions that do not result in hospitalization, or development of drug dependency or drug abuse.

- Progression of the malignancy under study (including signs and symptoms of progression) should not be reported as an SAE unless the outcome is fatal within the active collection period. Hospitalization due to signs and symptoms of disease progression should not be reported as an SAE. If the malignancy has a fatal outcome during the study or within the active collection period, then the event leading to death must be recorded as an AE on the CRF, and as an SAE with CTCAE Grade 5 (see the Assessment of Intensity section).

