7.4.1. Time Period and Frequency for Collecting AE and SAE Information

The time period for actively eliciting and collecting AEs and SAEs ("active collection period") for each patient begins from the time the patient provides informed consent, which is obtained before the patient's participation in the study (ie, before undergoing any study-related procedure and/or receiving study treatment), through and including a minimum of 30 calendar days, except as indicated below, after the last administration of the study treatment.

During the long-term follow-up period in this study for survival, only SAEs will be actively elicited and collected after completion of the active collection period described above. The SAEs identified during long-term follow-up will be reported to Pfizer Safety on the CT SAE Report Form only if considered reasonably related to the study treatment.

Follow-up by the investigator continues throughout and after the active collection period and until the AE or SAE or its sequelae resolve or stabilize at a level acceptable to the investigator and Pfizer concurs with that assessment.

For patients who are screen failures, the active collection period ends when screen failure status is determined.

If the patient withdraws from the study and also withdraws consent for the collection of future information, the active collection period ends when consent is withdrawn.

If a patient definitively discontinues or temporarily discontinues study treatment because of an AE or SAE, the AE or SAE must be recorded on the CRF and the SAE reported using the CT SAE Report Form.

Investigators are not obligated to actively seek AEs or SAEs after the patient has concluded study participation. However, if the investigator learns of any SAE, including a death, at any time after a patient has completed the study, and he/she considers the event to be reasonably related to the study treatment, the investigator must promptly report the SAE to Pfizer using the CT SAE Report Form.

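### Protocol Appendix 7, section 7.2, both excludes and requires an SAE record for death from disease progression, so descriptive serious and Grade 5 TEAE rates can depend on which line a site follows

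*Protocol*

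**What the plan says.** Protocol Appendix 7, section 7.2, begins with a general rule: if something is not an AE under the preceding definition, "then it cannot be an SAE even if serious conditions are met". The examples in brackets are "hospitalization for signs/symptoms of the disease under study, death due to progression of disease".

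Item f of the same section says that progression of the malignancy "should not be reported as an SAE unless the outcome is fatal within the active collection period". Two sentences later it sets a duty to record: "the event leading to death must be recorded as an AE on the CRF, and as an SAE with CTCAE Grade 5". The window attached to that duty is wider than the one just given: "If the malignancy has a fatal outcome during the study or within the active collection period".

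Protocol section 7.4.1 runs the active collection period from informed consent "through and including a minimum of 30 calendar days" after the last dose. SAEs found in long-term survival follow-up go to the sponsor's safety group only if judged related to treatment.

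In Appendix 7, section 7.1, the list of events that do not meet the AE definition includes "The disease/disorder being studied or expected progression, signs, or symptoms of the disease/disorder being studied, unless more severe than expected", judged against how the individual patient is doing. The last bullet of that list says: "Worsening of signs and symptoms of the malignancy under study should be recorded as AEs in the appropriate section of the CRF".

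SAP section 6.6.1 uses seriousness and grade as the investigator enters them. It tabulates serious TEAEs, TEAEs of Grade 3 or higher, and TEAEs by maximum grade. It has no rule for fatal progression events.

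**The concern.** For one event, death from progression while the patient is under active AE collection, one line of section 7.2 rules out an SAE and another demands one at Grade 5. A careful investigator could follow either. The study may use up to 75 centers, and the SAP neither re-adjudicates nor separates these events, so the tables could combine sites that record them with sites that do not.

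AE incidence and severity is a stated endpoint in both study parts. The protocol also allows treatment to continue after progression in one compartment (section 6.8), so some post-progression time can fall inside the TEAE window. What is at stake is whether the descriptive safety rates mean the same thing from site to site.

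**Working it through.** The plan states no expected rate of SAEs or Grade 5 events, so there is no figure to reproduce. The check is a comparison of the texts, followed by simple arithmetic under a stated assumption.

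**Step 1: the instructions side by side.**

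| Event | Appendix 7, 7.2, opening | Appendix 7, 7.2, item f | Protocol 7.4.1 |
|---|---|---|---|
| Progression death within the active collection period | Not an SAE | AE and Grade 5 SAE | Sets the period; does not say whether this event is an SAE |
| Progression death later, in survival follow-up | Not an SAE | Not an SAE by its first sentence; Grade 5 SAE by its last | Reported only if related to treatment |

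The first row is a direct conflict. The second row shows that item f also disagrees with itself and with section 7.4.1.

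**Step 2: the route into the analysis.**
- SAP section 3.4.1: a TEAE starts on or after first dose and before last dose + 30 days, or before subsequent anticancer drug therapy, whichever is earlier.
- SAP section 3.4: safety data outside the on-treatment period are listed only.
- SAP section 6.6.1: seriousness and grade are the investigator's.

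Only fatal events with onset inside the TEAE window can therefore move the tabulated rates.

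**Step 3: what cannot move.**
- DLTs: Protocol Table 7 and SAP section 3.1.1 exclude events explained by disease progression.
- BMRR: based on tumor assessments.
- OS: based on date of death.
- The death table (SAP section 6.6.2): built from the death and disposition eCRFs.

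**Step 4: size under an assumption.** Let k be the number of progression deaths in the TEAE window recorded under one reading and not the other, and n the number of patients. The largest change in the Grade 5 rate is k/n. The documents do not give k; I assume 1 to 5.
- n = 50 (the full cohort size in SAP section 5.1.2.2): 1/50 = 2 points, up to 5/50 = 10 points.
- n = 100 (both cohorts full): 1/100 = 1 point, up to 5/100 = 5 points.

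These are upper limits, with every site on one reading set against every site on the other. A mix of sites falls between. The serious and Grade 3 or higher rates move by no more than this, and by less where the patient already has another such event. The gap also shrinks where worsening symptoms were recorded as an AE under section 7.1 and proved fatal, because an AE that results in death is serious under section 7.2(a) on either reading.

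**The case against.** The strongest reply is that the operative rule can be found. Item f is the specific instruction, with an express exception and a mandatory verb. The opening sentence is conditional, so once item f makes the event an AE the condition is not met. Protocol section 7.4.7, on disease-related outcomes that do not qualify as AEs or SAEs, reads not applicable, which also favors item f.

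This is a plausible reading and probably the intended one, but it does not remove the conflict. The opening sentence points back to the definition before it, where expected progression is listed as not an AE, and it names this exact case. Specificity therefore does not decide between the two lines, and no precedence is stated.

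Other parts of the defense stand:
- The two section 7.1 bullets are largely reconcilable. Expected symptoms are not AEs, while worsening ones are. The second bullet is mainly misplaced under its heading.
- TEAEs are tabulated by preferred term and deaths by primary cause, so a reader can see recorded progression terms as separate rows. That does not recover events a site never recorded as AEs.
- AE rates carry no hypothesis test, and no formal comparison of the cohorts is planned.

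A reader might infer that the Grade 5 rate swings from zero to tens of percent. The documents give no count of progression deaths to support that, and zero is unsafe as the lower end because of the worsening-symptom route. A reader might also infer that the lead-in dose decision is compromised. It rested on DLTs, and SAP version 2.0 already reports its outcome. Nor does the wider window in item f bring later-onset events from survival follow-up into the TEAE tables; the SAP's windows keep them out.

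**Conclusion.** The contradiction is real and sits in the current text of one section. Its reach is limited to the descriptive serious, Grade 3 or higher and maximum-grade TEAE rates. It falls mainly on Phase 2, because Appendix 7 entered with Amendment 3 in August 2020 and the lead-in DLT result was known by SAP version 2.0 in September 2020.

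The 2 to 10 points per cohort of 50 rests on an assumed 1 to 5 deaths, all recorded under one reading and missed under the other. The documents do not show that any site has followed the opening line. The point is worth correcting because it affects how on-treatment deaths are recorded and the remedy is small.

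**What to change.** Reconcile Appendix 7, section 7.2 (opening sentence and item f), with Protocol section 7.4.1, so that there is one recording rule and one window. One way is to delete death from progression from the bracketed examples in the opening sentence and to limit item f to the active collection period. Move the worsening-symptoms bullet in section 7.1 out from under the heading for events that are not AEs. Send sites a clarification.

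As an optional presentation aid, SAP section 6.6.1 could show serious and Grade 5 TEAEs with and without disease-progression preferred terms.

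The cost is a wording amendment and a site memo. If sites have already recorded such deaths differently, some completed AE and SAE forms may need queries. No new patient assessments are required.
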